3.2 DRUG AND VACCINE ADMINISTRATION

3.2.1 Antiretroviral Therapy

Patients in Cohort 1 are required to be on a stable, combination highly active antiretroviral regimen based on current Department of Health and Human Services (DHHS) Guidelines for treatment of HIV infection⁹⁸ for \geq 6 months with CD4 and viral load parameters at entry as specified in the inclusion criteria (2.1.1.5). Whenever possible, changing antiretroviral therapy should be avoided unless needed for optimal patient care. Antiretroviral drugs obtained through expanded access programs are permitted.

3.2.2 Quadrivalent HPV (types 6, 11, 16, 18) Recombinant Vaccine Administration

Quadrivalent HPV vaccine will be administered intramuscularly as 3 separate 0.5ml doses, in single use, prefilled syringes at 0, 2 and 6 months (\pm 2 weeks) in an outpatient clinic setting. Vaccine should be administered intramuscularly in the deltoid region of the upper arm or in the higher anterolateral area of the thigh. Thorough agitation immediately before administration is necessary to maintain suspension of the vaccine. Following thorough agitation, the vaccine is a white cloudy liquid. The vaccine should not be administered if particulate matter is present or if it appears discolored. Patients will remain under nursing observation for 2 hours following the first injection. Vaccine-related adverse reactions will be evaluated using vaccination report card (VRC)-aided surveillance for 14 days after each dose of quadrivalent HPV (types 6, 11, 16, 18) recombinant vaccine in all study subjects. Per the ACIP Recommendations for the Use of Quadrivalent HPV Vaccine, the vaccine can be administered at the same visit when other age appropriate vaccines are indicated, such as Tdap, Td and MCV4.⁸⁴ Study subjects with minor acute illnesses e.g. upper respiratory tract infections or diarrhea with a temperature $< 101^{\circ}\text{F}$, will be allowed to receive vaccine. Vaccination will be deferred for individuals with moderate or severe acute illnesses and/or temperature $\geq 101^{\circ}\text{F}$ until after the illness resolves.

3.3 TREATMENT MODIFICATIONS

3.3.1 Antiretroviral Therapy

Cohort 1 HIV-Infected Patients on HAART

In the event that a *change* in antiretroviral therapy is warranted based on clinical, immunologic (CD4 count) or viral (HIV-1 RNA levels) parameters, regimen changes will be:

- Made after non-adherence to the current treatment regimen has been *ruled out* as a reason for the observed changes in clinical, immunologic or viral parameters warranting the change in therapy.
- Implemented according to principles and recommendations outlined in the DHHS treatment guidelines.⁹⁸
- Managed by the patient's referring physician in consultation with the protocol team.

Patients that require a *change* in their antiretroviral treatment regimen *prior to study month 7* and completion of all three quadrivalent HPV vaccinations will be taken off study and will not count towards the accrual ceiling for Cohort 1. Up to 10 additional patients will be allowed to enroll in Cohort 1 as replacements to reach the intended Cohort 1 N= 35. Patients that require a *change* in their antiretroviral treatment regimen *after study month 7* following completion of all three quadrivalent HPV vaccinations will be allowed to remain on study.

In the event that a *substitution* in antiretroviral therapy is warranted based on antiretroviral drug toxicity, regimen changes will be:

- Implemented according to principles and recommendations outlined in the DHHS treatment guidelines.⁹⁸

Patients that require a *substitution* in their antiretroviral treatment regimen, whether *prior to* or *after* completion of all three quadrivalent HPV vaccinations will be allowed to remain on study.

Cohort 2 HIV-Infected Patients on No Therapy

In the event that *initiation* of antiretroviral therapy is warranted based on clinical, immunologic (CD4 count) or viral (HIV-1 RNA levels) parameters, antiretroviral treatment will be:

- Implemented according to principles and recommendations outlined in the DHHS treatment guidelines.⁹⁸
- Managed by the patient's referring physician in consultation with the protocol team.

Patients that require *initiation* of antiretroviral treatment *prior to study month 7* and completion of all three quadrivalent HPV vaccinations will be taken off study and will not count towards the accrual ceiling for Cohort 2. Up to 10 additional patients will be allowed to enroll in Cohort 2 as replacements to reach the intended Cohort 2 N= 35. Patients that require *initiation* of antiretroviral treatment *after study month 7* following completion of all three quadrivalent HPV vaccinations will be allowed to remain on study.

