6.3 PRIMARY VIROLOGIC SAFETY ANALYSIS

Are HIV-1 RNA levels equivalent among HIV-infected patients on HAART versus those not on HAART following vaccination between baseline and timepoint X?

The statistical analysis assumes that an equivalence test will be used, and that no more than 5% of HIV-infected individuals would experience a $\geq 0.5 \log_{10}$ (the range of biologic variation) increase in HIV-1 RNA levels within a week following vaccination or at subsequent time-points. The primary goal of this statistical safety analysis is to determine whether the fraction of patients experiencing a $\geq 0.5 \log_{10}$ increase in HIV-1 RNA levels *at any time within the first week* and up to 1 year following the first immunization, may be considered equivalent between those HIV-infected individuals receiving HAART and those not on HAART following receipt of quadrivalent HPV vaccine. Time-point 1 comparisons of changes in the peak HIV-RNA levels from day 1 between Cohort 1 and 2 during any of the evaluations during the first week (see below) will be considered as the most important primary evaluation for this equivalence study and will be the basis for sample size determination. Another primary evaluation will be based on determining the equivalence of the fractions with day 7 vs. day 1 levels $\geq 0.5 \log_{10}$ (the range of biologic variation) increase in HIV-1 RNA levels between the two cohorts.

Equivalence tests can require a tremendous number of subjects in order to allow only a small interval of difference to be interpreted as equivalent. In order to allow for the test to be done with a moderate number of patients, the two vaccine cohorts will be considered equivalent if the fraction of vaccine recipients in one cohort who have an HIV-1 RNA level increase $\geq 0.5 \log_{10}$ is within 10% of that of the other cohort. Thirty-five patients are required per arm within each HIV-infected cohort, to have 73% power to document this level of equivalence. Formally stated, 35 patients per arm was selected as the sample size in order to allow a single two-group t-test of proportions with a one-sided 0.10 significance level to have 73% power to reject the null hypothesis that the two cohorts are not equivalent with respect to the fraction of patients experiencing a $\geq 0.5 \log_{10}$ increase in HIV-1 RNA levels *at each individual time comparison--the maximum increase within the first week* and up to 1 year following the first immunization.

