Timepoints for HIV-1 RNA Level Analysis: Comparison between Recipients in HIV-Infected Cohorts 1 and 2:

- Timepoint 1 Day 1 vs. Day 3 or Day 7 (immediately s/p vaccination) (*primary*)
- Timepoint 2 Day 1 vs. mos 1 (1mos s/p 1 vaccination)
- Timepoint 3 Day 1 vs. mos 3 (1mos s/p 2 vaccinations)
- Timepoint 4 Day 1 vs. mos 7 (1mos s/p 3 vaccinations)
- Timepoint 5 Day 1 vs. mos 12 (6mos s/p 3 vaccinations)

Within each cohort, the change in \log_{10} HIV-1 RNA levels will be determined between day 1 and day 7 and will be evaluated to see if the values at the two time points are not statistically different from one another. HIV-1 RNA levels below the lower limits of detection (50 copies/ml) will be expressed as 1.69 \log_{10} on a logarithmic scale equivalent to 49 copies/ml. With a minimum of 27 patients in each cohort of HIV-infected individuals, there is at least 95% power to detect a change from day 1 to day 7 with an effect size of 1 SD and a 0.025 two-sided alpha level test (0.05/2cohorts) after allowing for a Bonferroni adjustment.

In addition, as a secondary evaluation, comparison of changes in HIV-1 RNA levels will also be done among the two cohorts from day 1 to day 7, and months 1, 3, 7 and 12 in order to assess if the change in level may have some association with the cohort in which the patient is enrolled. This evaluation will be considered exploratory for all comparisons and timepoints.

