Potential risks include unknown or excessive adverse events related to the safety of the vaccine. This is unlikely to occur because the vaccine is not comprised of live, attenuated or inactivated viruses but rather of highly purified, recombinant virus-like particles (VLPs) of the major capsid (L1) protein of HPV types 6, 11, 16 and 18.⁷⁹ In addition, the FDA did not require the pharmaceutical manufacturer to present evidence of safety in immunocompromised populations as a condition for vaccine approval and licensure, and current ACIP Recommendations for use of the vaccine endorse its use in immunocompromised females, with the caveat that the immune response to vaccination and vaccine effectiveness might be less than in females who are immunocompetent.⁸⁴ Another potential risk is the upregulation of HIV viral replication associated with vaccine administration. Although likely to be minimized by HAART, it could potentially be more of an issue in those receiving no antiretroviral therapy. Entry criteria parameters were established such that if increases in viral replication were to be observed associated with vaccination, it would be in individuals with HIV-1 RNA levels \leq 20,000 copies/ml at entry with no indication for initiation of antiretroviral therapy i.e. HIV-1 RNA levels \geq 100,000 that are associated with higher risk for disease progression.⁸⁵

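### The accrual halt in 6.7 can miss patients who meet its own criteria, and 6.3 has no rule for patients removed and replaced under 3.3.1

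*Combined protocol and SAP*

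**What the plan says.** **Removal and replacement (3.3.1).** In Cohort 1 the trigger is a change in ART that "is warranted based on clinical, immunologic (CD4 count) or viral (HIV-1 RNA levels) parameters, regimen changes will be" subject to listed conditions. If the change comes before month 7 and completion of the three doses, the patient "will be taken off study and will not count towards the accrual ceiling for Cohort 1. Up to 10 additional patients will be allowed" to bring the cohort back to 35. In Cohort 2, a patient who starts ART before month 7 on the same kinds of grounds "will be taken off study and will not count towards the accrual ceiling for Cohort 2", again with up to 10 replacements. Substitutions for drug toxicity stay on study. So do patients whose ART is changed or started after month 7.

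**Virologic safety (6.3).** The decision rule is that "the two vaccine cohorts will be considered equivalent if the fraction of vaccine recipients in one cohort who have an HIV-1 RNA level increase" of at least 0.5 log10 lies within 10% of the other cohort's fraction. The sample size rests on "a single two-group t-test of proportions with a one-sided 0.10 significance level to have 73% power". The first-week comparison is marked primary. Later ones follow at months 1, 3, 7 and 12, for example "Timepoint 4 Day 1 vs. mos 7 (1mos s/p 3 vaccinations"). No analysis set is defined, and patients removed under 3.3.1 are not mentioned.

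**Halt rule (6.7).** Accrual to the HIV-infected cohorts stops if 3 or more patients in one cohort, or 5 or more across both, are removed from study before month 12 for CD4 decline or HIV-1 RNA increase. The criteria are cited as 3.9.7 and 3.9.8. Section 3 ends at 3.8; the matching criteria are the seventh and eighth bullets of 3.7. Both are labelled Off Treatment and need two measurements 4 weeks apart.

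**The concern.** There are two linked gaps.

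First, 6.7 counts an administrative outcome (leaving the study), while the criteria it points to lead, by their labels, only to stopping vaccine. Other bullets in 3.7 carry both labels, so the difference looks deliberate to someone applying the text. Section 6.7 itself treats these events before month 12 as a possible sign of excess virologic risk, and 7.5.1 provides no independent monitor or DSMB. The tally should therefore count the patients it is meant to count.

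Second, removal under 3.3.1 can be prompted by a rise in HIV-1 RNA, which is the outcome compared in 6.3. Replacing such a patient with one who has had no rise lowers the observed fraction. If the retained 35 per cohort became the analysis set, the month 1–12 comparisons would be biased toward no harm. Those comparisons belong to the stated goal of covering up to one year. They carry extra weight in practice because Appendix 2A lists no HIV-1 RNA draw between screening and month 1.

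**Working it through.** **1. The plan's own figure.** Inputs from 6.3: 35 per cohort, 5% with a rise in each, margin 0.10, one-sided 0.10 (z = 1.2816).

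- SE = √(2 × 0.05 × 0.95 / 35) = 0.0521.
- Power = Φ(0.10/0.0521 − 1.2816) = Φ(0.638) = 0.738. Exact binomial enumeration gives 0.747. The plan states 73%, so the figure reproduces.

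**2. Who the halt tally can miss.** Reading 6.7, 3.7 and 3.3.1 together, a patient can meet the CD4 or HIV-1 RNA criterion before month 12 and not be counted in three ways:

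- The patient goes off treatment under 3.7 but stays on study. After the month 6 dose there is no vaccine left to stop, so the label has no visible consequence.
- ART is changed or started after month 7, and 3.3.1 keeps the patient on study.
- ART is changed or started before month 7, and the exit is logged under 3.3.1.

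A patient may also exit under 3.3.1 before the 4-week confirmation.

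Sensitivity of the rule, by exact binomial with 35 per cohort (halt at 3 or more in either, or 5 or more in total), ignoring replacements. Both the qualifying rate and the missed share are assumptions.

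| True qualifying rate | All counted | 25% missed | 50% missed | 75% missed |
|---|---|---|---|---|
| 5% | 0.44 | 0.27 | 0.11 | 0.02 |
| 10% | 0.91 | 0.74 | 0.44 | 0.11 |

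**3. Effect of replacement on 6.3.** Let p be the true fraction with a rise at a later timepoint, and r the share of those patients removed and replaced. The fraction among the retained 35 is p(1 − r)/(1 − pr). Assume 5% in Cohort 1 (the plan's maximum) and 20% in Cohort 2, an excess of 15 points against a 10-point margin. The test declares the Cohort 2 excess within the margin if d + 1.2816 × SE (unpooled) < 0.10, enumerated exactly for 35 versus 35.

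| r | Cohort 1 observed | Cohort 2 observed | P(wrong declaration), both cohorts lose patients | P, only Cohort 2 loses patients |
|---|---|---|---|---|
| 0 | 0.050 | 0.200 | 0.036 | 0.036 |
| 0.10 | 0.045 | 0.184 | 0.049 | 0.056 |
| 0.25 | 0.038 | 0.158 | 0.079 | 0.105 |
| 0.50 | 0.026 | 0.111 | 0.192 | 0.287 |
| 0.75 | 0.013 | 0.059 | 0.486 | 0.672 |

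In the last column Cohort 1 stays at 0.050.

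With Cohort 2 at 15% (on the margin), the error with removal in both cohorts goes from 0.126 to 0.153–0.210 for r = 0.10–0.25. With Cohort 2 at 25% it goes from 0.009 to 0.013–0.025. At 5% in both cohorts, equal removal creates no difference.

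Replacements needed in Cohort 2 at 20% are 35/(1 − 0.20r) − 35 = 1.8, 3.9 and 6.2 for r = 0.25, 0.50 and 0.75. All are under the cap of 10.

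**4. With all dosed patients kept and rises before removal counted.** True rates of 5% and 20% with 35/37, 36/39 and 36/41 patients (r = 0.25, 0.50, 0.75) give 0.030, 0.032 and 0.031. The error no longer depends on r.

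**The case against.** **On 6.7.** The criteria can be found: bullets seven and eight of 3.7 match the numbering, and 6.7 names that section's title, so only the 3.9 is wrong. The labels are also loose, since the pregnancy bullet says Off Treatment and then takes the patient off study. A sensible reader might count every qualifying patient, including a 3.3.1 exit prompted by CD4 or RNA. This stands as far as it goes: a miss is possible, not certain, and a reader should not infer that the rule has no criteria. It does not remove the problem, because the words tie the count to study removal and 3.3.1 keeps later ART changes on study.

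**On 6.3.** The accrual-ceiling sentence is an enrolment rule, and the denominator is described as vaccine recipients, which can include removed patients. That is right. The documents do not say they are excluded; they are silent.

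**On removal being the outcome itself.** A reader might infer that every Cohort 2 patient removed on RNA grounds is automatically a 6.3 event. Section 8.3 describes patients "at entry with no indication for initiation of antiretroviral therapy i.e. HIV-1 RNA levels" of 100,000 copies/ml or more, and log10(100,000/20,000) = 0.70 exceeds 0.5. But 20,000 is a screening ceiling, and 6.3 measures from Day 1 at set visits. Such a patient will usually, but not by definition, be an event. ART may also be started on CD4 or clinical grounds with no RNA rise.

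**On size.** The large error rates need removal shares of 50–75%, which the documents do not support. Section 3.2.1 says "Whenever possible, changing antiretroviral therapy should be avoided unless needed for optimal patient care", 3.3.1 requires non-adherence to be ruled out first, and 8.3 puts the starting level high. At 10–25% removal in both cohorts the error in the 5% versus 20% case stays below the plan's 0.10. A single share for every timepoint is also a simplification, since little removal precedes month 1.

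**On importance.** Only the first-week comparison is marked primary, the comparison of changes in level is labelled exploratory, and 7.5.1 provides data review at least monthly. These points limit the weight of the concern but supply neither missing rule.

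**Conclusion.** The concern holds in a limited form and should be fixed.

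- The halt rule, followed literally, can undercount patients who meet its criteria before month 12. This rests on the text alone. How many would be missed cannot be derived from the documents.
- Section 6.3 leaves open how patients removed under 3.3.1 enter the month 1–12 comparisons. If only the retained 35 per cohort were analysed, the bias would be toward no harm. On the assumed 5% versus 20%, the effect at plausible removal shares (10–25%) is modest: 0.036 to 0.049–0.079, or 0.056–0.105 if only Cohort 2 loses patients. The true rates and removal shares are assumptions.

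The documents do not support saying that removed patients are excluded, or that an equivalence finding would be wrong half the time. The plan's 73% power is not in dispute.

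**What to change.** **Section 6.7.** Change the reference to 3.7. Count every HIV-infected vaccinated patient who meets the CD4 or HIV-1 RNA criterion before month 12, whether off treatment, off study, exited under 3.3.1 or still on study. Report unconfirmed RNA- or CD4-driven 3.3.1 exits beside the tally, without adding them to the thresholds of 3 and 5. The rule is already sensitive: background rates of 2.5% and 5% per cohort give halt probabilities of 0.11 and 0.44.

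**Section 6.3.** Analyse all HIV-infected patients given at least one dose, including those later replaced. For months 1–12, count a patient removed under 3.3.1 as an event at later timepoints in either of two cases: a rise of at least 0.5 log10 from Day 1 was recorded at any visit before the ART change or start, or that change was RNA-driven. Do not use RNA values taken after the change or start to classify a patient as a non-event; the off-study sample in 3.8, taken within 8 weeks of removal, may already be suppressed. Show the per-timepoint comparison of observed values as a sensitivity analysis.

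**Cost.** Protocol and SAP wording only; no new visits or samples. The safety estimate may look slightly worse, and the halt may trigger somewhat more often.

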3.4 PHARMACOKINETIC STUDIES

As this is a vaccine study, no pharmacokinetic studies will be performed.

3.5 ON STUDY EVALUATION (REFER TO APPENDICES 2 AND 3)

All study visits for this protocol will be performed at the NIH Clinical Center in Bethesda, MD.

3.5.1 Vaccine Study Visits: Months 0, 2 and 6 (\pm 2 weeks)

3.5.1.1 Clinical Evaluation

- 3.5.1.1.1 Review of systems and documentation of symptoms.
- 3.5.1.1.2 Specifically document as present or absent: fever \geq 101°F, malaise, headache, rash, or other signs or symptoms of acute illness.
- 3.5.1.1.3 Height and weight.
- 3.5.1.1.4 Vital signs.
- 3.5.1.1.5 Directed physical examination including skin exam and lymph node survey and documentation of any abnormalities.
- 3.5.1.1.6 Provision of Vaccination Report Card (VRC) to study subject.

3.5.1.2 Laboratory Evaluation

- 3.5.1.2.1 CBC with differential
- 3.5.1.2.2 Acute panel

- 3.5.1.2.3 Hepatic panel
- 3.5.1.2.4 Mineral panel
- 3.5.1.2.5 Serum pregnancy test in post-menarchal females
- 3.5.1.2.6 CD4 percent and absolute cell count

3.5.1.3 Research Evaluations (refer to Appendices 5 and 6)

- 3.5.1.3.1 HPV DNA Testing (Month 0 only, all subjects) performed by Roche Molecular Diagnostics, [name].
 - 3.5.1.3.1.1 Cytobrush in PreservCyt (10ml)
 - 3.5.1.3.1.2 External anogenital sampling: Medscand Cytobrush® Plus (CooperSurgical, <http://www.coopersurgical.com>)
 - 3.5.1.3.1.2.1 Females Brush 1: labia prepuce and external vulva Brush 2: anogenital junction
 - 3.5.1.3.1.2.2 Males Brush 1: glans, coronal sulcus, and scrotum Brush 2: anogenital junction
- 3.5.1.3.2 Serum for HPV antibody titers performed by Merck (Month 0 only, all subjects. Competitive luminex assay). 10ml RTT
- 3.5.1.3.3 Studies to be performed by [name], NCI, Frederick (Month 0 only, all subjects):
 - 3.5.1.3.3.1 Functional HPV antibody neutralization assays.
 - 3.5.1.3.3.2 Cryopreserved PBMCs (6 tubes 10ml sodium heparin GTT) for:
 - 3.5.1.3.3.2.1 HPV & HIV lymphocyte proliferation assays
 - 3.5.1.3.3.2.2 Cytokine induction assay
 - 3.5.1.3.3.2.3 Luminex multi-cytokine profiling of PBMCs
- 3.5.1.3.4 Extended FACS/Quantitative lymphocyte subpopulation studies: 10ml sodium heparin GTT (Month 0 only, HIV-infected subjects only)

Proposed 5 Color FACS Panel for Naïve & Memory Lymphocyte Subsets & Activation Markers

Tube #	AB1	AB2	AB3	AB4	AB5	Comment
1	CD45	CD14	CD3	CD56	CD19	
2	CD45	CD14	CD3	CD4	CD8	
3	HLA-DR	CD38	CD3	CD4	CD8	Activation CD4, CD8
4	IgG1	CD25	CD3	CD4	CD8	Activation CD4, CD8
5	CD27	CD45RO	CD3	CD4	CD8	Naïve, Central Memory, Effector Memory
Possible Additional Tubes for Subset Analysis						
6	CD45RA	CD31	CD3	CD4	CD8	Differential TREC levels
7	CD45RA	CCR7	CD3	CD62L	CD4	Naïve, Central Memory, Effector Memory*
8	CD45RA	CCR7	CD3	CD62L	CD8	Naïve, Central Memory, Effector Memory*

*Note: Must be performed on fresh PBMCs as CD62L is lost on frozen cells.

3.5.1.3.5 Serum Storage 10ml RTT (Leidos): for [name] functional HPV neutralization antibody assay and for possible later quantitative measurement of HIV-related chemokines MIP-1 α , MIP-1 β and RANTES

3.5.1.3.6 Whole blood for HPV DNA testing 6ml Dark Lavender K₂EDTA, collect 3 tubes (18ml total), Drs. [name] & [name] (Month 0 only)

3.5.1.3.7 Research assays immunologic responses 10ml sodium heparin GTT, collect 2 tubes (20ml total), [name]. (Months 0, 2 and 6 only, HIV-infected subjects only)

3.5.1.3.8 Administration of HPV/HIV knowledge and risk and sexual behavior surveys. (Month 0 only. **Refer to Appendices 7-10**)

3.5.2 Follow-Up Study Visits Year 1: Months 1, 3, 7 (\pm 2 weeks) and 12 (\pm 30 days)

3.5.2.1 Clinical Evaluation

3.5.2.1.1 Review of systems and documentation of symptoms.

3.5.2.1.2 Height and weight.

3.5.2.1.3 Vital signs.

3.5.2.1.4 Directed physical examination including skin exam and lymph node survey and documentation of any abnormalities.

3.5.2.1.5 Gynecologic evaluation, cervical cytology (Pap smear) and HPV DNA testing (Month 12 only, sexually active females only)

